5.1 Intention-To-Treat

All randomized participants will be evaluated according to the randomized group and assigned evaluation within that group (if any), regardless of testing or treatment received. Unless otherwise indicated, all primary summaries and analyses will be performed using this definition of treatment.

5.2 Per-Protocol

Clinicians have the option to pursue alternative diagnostic pathways if they deem it to be in the best interest of the participant, with the reason for study protocol deviation documented. The per-protocol treatment assignment is met when randomized participants received their initial evaluation as randomized. Trial participants who crossed over to the other randomized arm and those who were assigned to testing in either arm and who received no testing are excluded from analysis using this definition of treatment assignment. In addition, participants in whom all inclusion criteria were not present or in whom one or more exclusion criterion were present will be excluded from the per protocol population.

Per Protocol Definition

- Meets all inclusion/exclusion criteria
- Precision Care Participants
 - Low Risk
 - No testing OR
 - First test is a CTA
 - Elevated Risk
 - First test is a CTA
- Usual Care
 - No CTA performed < 45 days post randomization
 - Low Risk
 - First test is a Usual Care Test
 - Coronary angiography without noninvasive testing
 - Stress cardiac MRI
 - Stress echocardiography (exercise or pharmacologic stress)
 - Stress nuclear perfusion (MPI or PET; exercise or pharmacologic stress)
 - Treadmill ECG without imaging
 - Elevated Risk
 - First test is a Usual Care Test
 - Coronary angiography without noninvasive testing
 - Stress cardiac MRI
 - Stress echocardiography (exercise or pharmacologic stress)
 - Stress nuclear perfusion (MPI or PET; exercise or pharmacologic stress)
 - Treadmill ECG without imaging

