unlikely (by definition) to have significant obstructive CAD. The managing clinician is encouraged to treat them with guideline-recommended preventive care, anti-anginal medications and other medical therapy as deemed appropriate to their clinical circumstances. This is expected to control or eliminate symptoms in most participants. In the unlikely event that symptoms are intractable or accelerating, despite reasonable medical treatment or if other compelling reasons for additional evaluation are present, testing may be warranted.

Unless there are urgent or emergent indications to proceed with invasive testing, all such participants requiring testing should have a cCTA followed by selective FFR_{CT} rather than stress testing or elective invasive catheterization. cCTA with selective FFR_{CT} should only be pursued if the participant is having:

1. Unstable/accelerating symptoms (i.e. no longer falls into stable angina cohort)
2. Continued stable symptoms despite risk factor modification including:
 - a) Optimized blood pressure control with goal <130/80 mmHg
 - b) Optimized lipid management with high-intensity statin in appropriate patients
 - c) Optimized diabetes management with blood glucose control in appropriate patients
 - d) Antiplatelet therapy in appropriate patients
 - e) Tobacco cessation in patients who smoke
 - f) Lifestyle counseling regarding diet exercise and stress reduction
 - g) Anti-anginal therapy including utilization of beta-blockers, calcium channel blockers, short and long-acting nitrates, and/or ranolazine

The assignment to no immediate testing is not time limited and is valid for the duration of the participant's enrollment in the trial. Testing in such participants should be infrequent and the reasons for this will be carefully documented and monitored.

V.F. Participant Withdrawal

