The study intervention is the implementation of a precision evaluation strategy compared to usual care evaluation in non-acute chest pain participants with no history of CAD or recent testing whose clinicians recommend non-emergent non-invasive testing or ICA. Since all trial procedures represent standard of care for the eligible study population, there are no specific safety events associated with investigative procedures in this trial. However, there are known complications from these clinically recommended tests and procedures which are outlined below. These complications will be reported by site personnel.

For Precision Evaluation Strategy

For Guideline-recommended Medical Management

While participants assigned to the guideline-recommended care with no planned testing arm will have exceedingly low risk of events and are predicted to derive minimal or no value from noninvasive testing^{33, 34}, there is a very small risk of missing left main or 3-vessel disease for which revascularization may be life-prolonging.

For cCTA with selective FFR_{CT}:

Mild contrast reaction such as rash and hives.

1. Severe contrast reactions including anaphylaxis or death occurring within 24 hours of contrast administration.
2. Extravasation of contrast into the surrounding tissue of the extremity where contrast was administered intravenously.
3. Symptomatic bradycardia or hypotension in relation to beta blockade or nitrates administered for cCTA.
4. Acute bronchospasm following beta blockade administered for cCTA.

For Usual Care (noninvasive or invasive testing)

For exercise testing including during stress echo or stress nuclear (including PET):

1. Hypotension defined as systolic BP less than 80 mmHg or fall in systolic BP >20 mmHg
2. Stress-induced symptoms or ECG changes that do not resolve within 20 minutes
3. Rapid atrial fibrillation that does not slow or convert with standard interventions
4. Ventricular tachycardia
5. Hospital admission not otherwise captured by pre-specified study endpoints, due to one of the above

For stress nuclear (including PET):

1. Any adverse reactions potentially related to the use of vasodilators such as adenosine, regadenoson, or dipyridamole

For stress echo:

1. Any stress-induced wall motion abnormality that does not resolve within 20 minutes
2. Any adverse reaction to echo contrast
3. Any adverse reaction to dobutamine, including sustained ventricular tachycardia or other tachyarrhythmias

For stress cardiac MRI:

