9.5 Alternative Treatment Assignment Analyses

Five additional analysis will be performed on the primary endpoint to assess whether the intervention effect size estimates vary to a clinically relevant extent according to adherence to the protocol and/or management actually received. The five are as follows:

- Including only Intention-To-Treat participants from the low risk strata
- Including only Intention-To-Treat participants from the elevated risk or known atherosclerosis strata
- Including only Per-Protocol participants
- Including only Per-Protocol participants from the low risk strata
- Including only Per-Protocol participants from the elevated risk or known atherosclerosis strata

10. Planned Table of Contents for Analysis Tables and Figures

The following tables and graphs are required for the Clinical Study Report and trial outcomes analyses. All tables are listed here for completeness.

Standard conventions will be used in table display such that the following data columns will be included: “All Usual Care” including total and additional columns of usual care split into “Low Risk” and “Elevated Risk”; “All precision care” columns will include total and additional as assigned columns indicated as “No Testing” and “CTA.”

Table/Graph Number	Table/Graph Title
Table 1.1	Participant Disposition All Randomized Participants
Table 2.1	Participant Demographics All Randomized Participants
Table 2.2	Cardiovascular Disease History; atherosclerosis history and Cardiovascular Risk Factors and risk scores All Randomized Participants
Table 2.3	Presenting Symptoms All Randomized Participants
Table 2.4	Medical History/Past Surgeries/ All Randomized Participants
Table 2.5	Physical Examination at Baseline All Randomized Participants
Table 2.6	Rest ECG Findings at Baseline All Randomized Participants
Table 2.7	Laboratory Testing at Baseline All Randomized Participants
Table 2.8	Concomitant Cardiovascular Medications at Baseline All Randomized Participants
Table 2.9	Quality Of Life at Baseline All Randomized Participants
Table 2.10	Prevention Motivation at Baseline All Randomized Participants
Table 3.1	Summary of Follow-up Visits All Randomized Participants

Table/Graph Number	Table/Graph Title
Table 3.4	Flow Chart Diagnostic Testing, Escalation (precision arm only) All Randomized Participants
Table 3.4.1	Flow Chart 1st Diagnostic Testing Randomized Tests All Randomized Participants

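### The SAP 5.2 bullets drop deferred low-risk precision participants whose first test is an urgent catheterization, a pathway protocol V.E permits, so per-protocol membership depends on outcome and differs by arm

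*SAP*

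**What the plan says.** SAP 5.2 gives a general rule and then a bulleted definition. The general rule is: "The per-protocol treatment assignment is met when randomized participants received their initial evaluation as randomized". It adds that participants who crossed over, and "those who were assigned to testing in either arm and who received no testing are excluded from analysis".

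The bullets are narrower. A low-risk precision participant qualifies with no testing or if "First test is a CTA". There is no time window and no exception for urgency. An elevated-risk precision participant must have CTA first. In usual care, "Coronary angiography without noninvasive testing" is a qualifying first test in both risk groups, whatever the indication and whatever test was intended.

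Protocol V.E (final version) says of participants assigned to no immediate testing: "Unless there are urgent or emergent indications to proceed with invasive testing, all such participants requiring testing should have a cCTA". It also says: "The assignment to no immediate testing is not time limited". SAP section 2 restates the CTA requirement for low-risk participants who come to need testing, but without the urgent exception.

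The per-protocol set is applied to the primary endpoint overall and within risk strata. SAP 9.5 lists "Including only Per-Protocol participants from the low risk strata", with outputs in Table 4.2.4.4 and Figure 4.2.2.4. SAP 5.1 makes intention-to-treat the primary basis.

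**The concern.** SAP 9.5 intends the per-protocol analyses to show whether the effect estimate changes with adherence. They cannot show that if adherent participants are removed because of what happened to them. A deferred participant who has an MI in month 8 and goes directly to catheterization has followed V.E, yet fails both low-risk routes.

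The time at risk of exclusion also differs. Usual-care participants are scheduled for a first test before the 45-day visit, so a later emergency catheterization is not their first test and cannot change their status. A deferred participant's first test can fall at any point in follow-up.

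The low-risk comparison matters most here. Protocol III.A calls safe deferral of testing in low-risk patients a core secondary objective, and protocol VII.C acknowledges that "there is a very small risk of missing left main or 3-vessel disease for which revascularization may be life-prolonging".

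**Working it through.** No figure in the plan bears on this definition, so there is nothing to reproduce. The check applies the SAP 5.2 text to each pathway, assuming eligibility is met and no early CTA was done in usual care.

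| Pathway | Per-protocol status under the bullets and exclusions |
|---|---|
| Low-risk precision, first test is urgent catheterization | Out under the bullets; in on a natural reading of the prose; permitted by V.E |
| Usual care, first test is catheterization for any reason | In |
| Low-risk precision, death or MI with no test | In |
| Usual care, death or MI with no test | Out, as untested |
| Elevated-risk precision, death or MI with no test | Out, as untested |
| Low-risk precision, event after a first CTA | In |
| Elevated-risk precision, first test is catheterization | Out; the V.E exception does not cover this group |

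Row 1 against row 2 removes precision events. Row 3 against row 4 removes usual-care events. Membership depends on post-randomization events in both arms.

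**Size in the low-risk precision group.** Inputs: 1050 per arm and about 20% low risk (SAP 7); CV death/MI below 1% per year in this risk category (protocol IX.B). The documents do not give the share f of these events in which urgent catheterization is the first test, so f is an assumption.

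- Participants: n = 1050 × 0.20 = 210.
- Expected events at the 1% upper bound: D = 210 × 0.01 = 2.1. At 0.5% and 0.25%, D is 1.05 and about 0.5.
- Events removed = D × f. The apparent ratio, if the true low-risk ratio is 1 and usual care is untouched, is [D(1 − f)/(n − Df)]/0.01.

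| Assumed f | Events removed | Apparent death/MI ratio |
|---|---|---|
| 25% | 0.525 | (1.575/209.475)/0.01 = 0.75 |
| 50% | 1.05 | (1.05/208.95)/0.01 = 0.50 |
| 75% | 1.575 | (0.525/208.425)/0.01 = 0.25 |

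**Size in the overall per-protocol set.** The planned rates are 5% and 8%, a ratio of 0.625, with 0.05 × 1050 = 52.5 precision events.

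- Removing 2 precision events: [(52.5 − 2)/(1050 − 2)]/0.08 = 0.602.
- If 10 catheterization-first participants each carried any primary event: [(52.5 − 10)/(1050 − 10)]/0.08 = 0.511.
- Opposite direction, removing 2 of the 0.08 × 1050 = 84 usual-care events as untested: 0.05/[(84 − 2)/(1050 − 2)] = 0.639.

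The last line shows only that the two asymmetries pull opposite ways. The documents do not say how many participants fall under each.

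**The case against.** The strongest reply is that these analyses are supplementary and that low-risk outcomes are already reported free of the exclusion. SAP 9.3.4.2 specifies the intention-to-treat low-risk comparison with its components (Table 4.13.1 and Figures 4.13.1.1 to 4.13.1.4). The listed per-protocol low-risk outputs are a composite Cox table and a forest plot, with no separate death/MI table. This stands and limits the importance of the point. It does not make the per-protocol set sound.

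A second reply is that the 5.2 prose already keeps the deferred participant, or that V.E governs. The prose does support this, but the bullets say otherwise, and SAP section 3 gives the SAP precedence over the protocol for analysis. An analyst could build two different sets from the same section.

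Several stronger readings are tempting, and the documents do not support them:

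- A reader might infer that the exclusion acts on one arm only and must favour precision care. The untested-participant rule removes usual-care events that would be kept in low-risk precision participants.
- A reader might infer that the harms of deferral vanish from the set. Deaths and MIs without a test, and events after a first CTA, all remain.
- A reader might picture 3 MIs in 210 becoming 0 in 207. That takes more events than the protocol's upper bound implies and sends every one straight to catheterization; no document gives that proportion.
- A reader might extend V.E to elevated-risk precision participants. Its exception covers only those assigned to no immediate testing, and protocol IV.G states no urgent exception to its conditions for angiography in the precision arm.

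Excluding elective catheterization without a prior CTA is ordinary per-protocol practice and is not criticised here.

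**Conclusion.** The point holds as a defect in the per-protocol definition. The bullets exclude a pathway that V.E permits and that the section's own prose would keep, while usual care retains the same pathway; the untested rule creates an asymmetry the other way. Membership therefore depends on outcome and differs by arm, with no established net direction.

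The primary and low-risk intention-to-treat results are not touched. Under the assumed f of 25–75%, about 0.5–1.6 low-risk precision death/MI events are removed. That barely moves the overall per-protocol ratio but could dominate a low-risk death/MI contrast, because only about 2 such events are expected at most. The estimate rests on the protocol's upper-bound rate (CV death/MI, not all-cause death/MI), the planned 20% low-risk share, and an f the documents do not supply.

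**What to change.** 1. In SAP 5.2, add a third qualifying route for low-risk precision participants: the first test is invasive angiography with a documented urgent or emergent indication under V.E. Elective non-CTA first tests remain deviations. Reconcile the 5.2 bullets with the 5.2 prose, SAP section 2 and V.E. This concerns who is counted in the analysis set and proposes no clinical rule.
2. For participants assigned to testing in either arm, do not treat a missing or different first test as a deviation when death or MI occurred before the initial test and within the period scheduled for it (before the 45-day visit). Limit this to death and MI. Catheterization without obstructive CAD is itself a primary-endpoint event, so a rule covering any primary event would keep an elective catheterization when no obstructive CAD is found and drop it when disease is found. That would be a new selection on outcome.
3. Report, by arm and risk stratum, the deaths, MIs and catheterization endpoints removed by each per-protocol exclusion.

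The cost is SAP wording, derived flags and a short table. V.E already requires the reasons for testing deferred participants to be documented. The small downside is that the indication for a few first catheterizations must be read from existing records.

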5.3 Subgroups of Intention-To-Treat and Per-Protocol

Four treatment comparisons will be made.

- Including only Intention-To-Treat participants from the low risk strata
- Including only Intention-To-Treat participants from the elevated risk or known atherosclerosis strata
- Including only Per-Protocol participants from the low risk strata
- Including only Per-Protocol participants from the elevated risk or known atherosclerosis strata

6. Participant Randomization and Enrollment

Once a participant has consented to participate in the trial, participant information will be entered in the database. If a patient is a screen failure, the data that have been collected up until this point for the patient for screening purposes will be entered into the eCRF in the EDC system. No additional information will be collected after this point for such a patient.

Participants who meet all inclusion criteria and none of the exclusion criteria will be randomized in a ratio of 1:1 within a clinical center to either of the following 2 groups using an IXRS.

Precision care - precision care strategy

Usual care- usual care strategy

Randomization will be stratified by intended first test assuming usual care (invasive vs. noninvasive) and by classification as low vs. elevated risk by the PROMISE risk model (see derivation below in Section 6.1). For testing purposes, participants with known non-obstructive coronary atherosclerosis or plaque will be assigned to the elevated risk strata regardless of risk score. The randomization scheme within a clinical center will be carried out by the method of random permuted block design. Participants will be randomized to either the usual care arm or the precision evaluation arm within 14 days of screening. The following tables summarizes the strata:

Summary of Strata

Strata	First Test	Risk
1	Non-Invasive	Low Risk
2	Non-Invasive	Elevated Risk or Known Atherosclerosis
3	Invasive	Low Risk
4	Invasive	Elevated Risk or Known Atherosclerosis

Enrollment in the randomization strata of intended first test being noninvasive (vs. invasive testing or direct to catheterization) will be capped at 90% of the sample size.

For eligible participants, medical history data will be captured in the EDC. In addition, sites will need to specify the intended first test that would be performed if the participant is randomized to the usual care arm. The participant will then be randomized to either the usual care arm or the precision evaluation arm. Once randomization occurs, the participant is considered enrolled in the study. If randomized to the precision evaluation arm, participants will be further assigned to guideline-recommended care without immediately planned testing or cCTA with selective FFR_{CT}.

Participants randomized to the usual care arm will undergo either noninvasive stress testing (exercise electrocardiogram, stress nuclear imaging including PET, stress MR, or stress echocardiogram), or invasive catheterization as the first evaluation, with the specific modality chosen at the discretion of the participant's clinician. Performance of cCTA or a calcium score as the initial test is excluded in this arm and prohibited as a subsequent test for the first 45 days after randomization.

Participants randomized to the precision evaluation arm will be assigned an initial evaluation and management approach based on their PROMISE risk score, a risk model based on pre-test clinical characteristics derived from the PROMISE trial and validated in SCOT-HEART, and presence of known mild atherosclerosis. Participants will be assigned to either guideline-recommended medical management without planned testing (low risk) or cCTA with selective FFR_{CT} (elevated risk or known including atherosclerosis; known mild atherosclerosis is defined as any of the following: non-obstructive CAD, CAC 0-99 HU, or unquantified coronary calcium seen on chest CT). Participants assigned to the strategy of no immediately planned testing and their providers will be given informational materials demonstrating the safety of this strategy based on pre-test probabilities and the PROMISE risk score. Participants with intractable

symptoms despite maximal medical management whose clinicians opt for further testing (escalation of care) will undergo cCTA with selective FFR_{CT}.

Participants undergoing cCTA as the initial test (both assigned or escalation) should have FFR_{CT} analysis ordered only if cCTA shows at least one 30-90% stenosis in epicardial vessels of 2 mm diameter or greater. Image sets will be sent promptly to HeartFlow for analysis and results will be returned to sites in less than 24 hours to enable rapid incorporation into clinical decision making.

Regardless of randomization or evaluation assignment, all participants will be treated with risk-appropriate preventive care and symptom control (including therapeutic trials of anti-anginal medications) as indicated.

6.1 Risk Groups based on PROMISE Risk Score

To calculate the PROMISE risk score use the following table estimates based on the risk score paper (Fordyce, JAMA Cardiology 2017). The Promise Score is equal to $1/(1+\exp(\text{logit}))$.

Logit Equation= $\gamma_1 + \gamma_2 * \text{Age (Years)} + \gamma_3 * \text{Sex(female=1)} + \gamma_4 * \text{Caucasian/Non-Hispanic (no=1)} + \gamma_5 * \text{Tobacco(current or former=1)} + \gamma_6 * \text{Diabetes(yes=1)} + \gamma_7 * \text{Dyslipidemia(yes=1)} + \gamma_8 * \text{Family history of premature (<55 years)Coronary artery disease(yes=1)} + \gamma_9 * \text{hypertension(yes=1)} + \text{Symptoms unrelated to physical or mental stress (not related=1)} + \gamma_{11} * \text{Symptoms unrelated to physical or mental stress(unknown=1)} + \gamma_{12} * \text{HDL (mg/dL)}$

Logit Equation coefficients

		HDL is available	HDL is not available	
			Female	Male
Intercept	γ_1	-3.7524	-3.7524	-3.7524
Age (Years)	γ_2	0.0842	0.0842	0.0842
Sex (female=1)	γ_3	-1.0264	-1.0264	-1.0264
Caucasian/Non-Hispanic (no=1)	γ_4	-0.1422	-0.1422	-0.1422
Tobacco (current or former=1)	γ_5	0.5264	0.5264	0.5264
Diabetes (yes=1)	γ_6	0.3141	0.3141	0.3141
Dyslipidemia (yes=1)	γ_7	0.4122	0.4122	0.4122
Family history of premature (<55 years) Coronary artery disease (yes=1)	γ_8	0.3086	0.3086	0.3086
Hypertension (yes=1)	γ_9	0.4078	0.4078	0.4078

Symptoms unrelated to physical or mental stress (not related=1)	γ_{10}	0.3086	-0.3086	-0.3086
Symptoms unrelated to physical or mental stress (unknown=1)	γ_{11}	-0.195	-0.195	-0.195
HDL (mg/dL)	γ_{12}	-0.00559	-0.318682 HDL constant	-0.252855 HDL constant

Risk groups will be defined as the following:

- Low Risk: Promise Score >0.46
- Elevated Risk: Promise Score ≤ 0.46

Low Risk and Elevated Risk groups are defined using a cut point based on the top 10% of low risk of the PROMISE Risk Score in the PROMISE cohort. Thus, in PRECISE, Low Risk is defined as an absolute score >0.46 .

7. Sample Size and Power Calculations

Sample size and power calculations for this study are based on the hypothesis that the precision evaluation arm is superior to the usual care arm on the time-to-first event of the composite 3-component endpoint: all-cause death, non-fatal MI, or invasive cardiac catheterization without obstructive CAD (obstructive CAD defined as diameter stenosis $\geq 50\%$, FFR ≤ 0.80 , or iFR ≤ 0.89) over a 12-month of follow-up. Time to event analysis will use the date of the event, including the date of catheterization at which the absence of obstructive CAD is demonstrated. Assuming 10% of usual care participants will receive angiography as a first test results in an 8% primary endpoint event rate at 1 year in the usual care group and 5% event rate in the precision care group (i.e., 3% absolute [37.5% relative] effect size). Assumptions used in the primary endpoint event rate calculations (i.e., 8% vs. 5%) were: overall 10% will not receive randomized evaluation, and within the precision evaluation arm, approximately 20% will be assigned to guideline-recommended care with symptom management and no planned testing, of whom about 30% will have escalation of care to cCTA with selective FFRCT.

Randomizing 1050 participants per group (2100 total participants) is estimated to provide at least 90% power to detect a relative risk reduction of 37.5% in the precision evaluation arm (see Table 1 below, or refer to the power curves in the protocol). Sample size/power calculations are based on the log-rank test with 12-month accrual period, a minimum 12-month follow-up (i.e. last participant will be followed for at least 12-months), 10% attrition rate (i.e. lost to follow-up, dropouts) and a two-sided type I error rate of 0.05.

The DSMB will review interim analysis data for efficacy as well as possible sample size re-estimation. At any interim analyses, the O'Brien-Fleming boundary generated by Lan-DeMets alpha-spending function will be utilized as a statistical stopping rule (See DSMB charter for more details).

Table 1. The total number of participants needed for 85%, 90%, and 95% power. Although this is not an event-driven study, the table below also provides total number of MACE needed.

1-year event rate in precision evaluation arm	Power	Total number of Primary Events needed	Total number of participants needed
(37.5% ^{2%} effect size)	85%	173	1792
	90%	202	2096
	95%	250	2592

8. Database Sources

There are several data sources and responsibility parties in PRECISE, as follows:

- All clinical data and angiographic core lab QCA results will be collected via EDC. Collection and data quality will be managed by Medpace and overseen by HeartFlow.
- The determination of the catheterization component of the primary endpoint is complex (see below section 9.2 for details). Briefly, clinical data present in the EDC will be extracted and processed through a HeartFlow Cath Algorithm to be classified as Obstructive CAD, No Obstructive CAD, Indeterminate (Require Medical Montior Review), CEC Adjudication Required, or Incomplete data. Each ICA classified as either Obstructive CAD, No Obstructive CAD, Indeterminate, or CEC Adjudication Required will undergo individual Medical Monitor review. For ICAs receiving a final classification as confirmed Obstructive CAD, No Obstructive CAD, or CEC Adjudication Required a signed Excel spread sheet will be transferred to CRF-NY and the data uploaded into a SAS data set for later transfer to DCRI. CEC Adjudication Required or Ambiguous ICAs will be adjudicated by the independent CEC. Data on Incomplete Caths will be queried and when complete, returned to the Cath Algorithm for repeat analysis.
- Results of CEC adjudicated clinical events and adjudicated ICAs receiving a final classification as confirmed Obstructive CAD or No Obstructive CAD will be entered into a separate EDC by CPC.

Table 2. Data sources and locations

Data Source	Data Location
All clinical data	Main Trial EDC managed by MedPace
CEC results	Database managed by CPC
Angio core lab	Main Trial EDC managed by MedPace
Cath Algorithm	Medical Monitor spreadsheet transferred into database managed by CRF-NY

Compilation of the trial's master analytic data set will require transfers of the databases from MedPace, CRF-NY, and CPC to the responsible party. All data from all sources will be combined into one analyzable master trial data set using SAS, which will in turn be shared with those responsible for trial analyses.

9. Statistical Analyses

